3.2 Study objectives

1. To determine change in number of pelvic adhesions based on MRI data in post-surgical period in comparison to data of pre-surgical MRI data
2. To determine change in thickness of pelvic adhesions based on MRI data in post-surgical period in comparison to data of pre-surgical MRI data
3. To determine frequency of limited displaceability of pelvic organs in post-surgical period (based on results of transvaginal ultrasound investigation).
4. To determine frequency of hyperechoic linear lesions in post-surgical period based on results of transvaginal ultrasound investigation.
5. To determine changes in frequency of detecting limited displaceability in comparison to baseline (absolute change and in % of baseline value).
6. To determine changes in frequency of detecting hyperechoic linear lesions based on repeated transvaginal ultrasound investigation in comparison to baseline.
7. To determine frequency of detecting complete absence of USI – signs of adhesion process in pelvis in post-surgical period (defined as absence of limited displaceability of pelvic organs and absence of hyperechoic linear lesions)
8. To determine number of adhesions during surgery.
9. To determine number of dense adhesions during surgery.
10. To determine percentage of female patients with any adverse reactions.
11. To determine percentage of female patients with any serious adverse reactions.
12. To determine percentage of female patients with adverse reactions, relation of which to use of the test drug or the placebo is “definite”, “probable” or “possible”.
13. To determine percentage of female patients with serious adverse reactions, relation of which to use of the test drug or the placebo is “definite”, “probable” or “possible”.
14. To determine percentage of female patients with mild adverse reactions.
15. To determine percentage of female patients with moderate adverse reactions.
16. To determine percentage of female patients with severe adverse reactions.
17. To determine percentage of female patients with clinically significant changes in results of physical examination.
18. To determine percentage of patients with clinically significant changes in vital signs.
19. To determine percentage of female patients with clinically significant changes in electrocardiogram (ECG).
20. To determine percentage of female patients with clinically significant laboratory parameters.

4 Design of the study

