8.2 Methods and terms of evaluation, recording and analysis of safety parameters

Evaluation of safety of the study drugs Seroguard, solution 0.41 g/L (JSC Pharmasyntez, Russia) and the Placebo will be performed for all the study subjects at Visits 1-3, based on account of parameter, specified in section 8.1. Detection of adverse reactions (ARs) happens from the moment of signing informed consent to visit 3 inclusive. In addition, each study subject will be provided a phone number of the Investigator for contact in case of any problems with health. Clinical symptoms that will be developed after signing informed consent, but before use of the test drug or the placebo will be recorded as concomitant disease.

If the Investigator finds/receives information on AR, an unscheduled visit at the study site will be appointed in the nearest time (if required). At the moment of receiving information on AR, after analysis of AR and evaluation of risk for the study subject, the Investigator comes to a decision on delivery of required medical care. At the unscheduled visit, the Investigator makes decision on possibility of further participation of female patient in the study.

In case of indications, by the decision of the Medical Investigator or the physician, additional clinical and/or laboratory-instrumental investigations may be performed at unscheduled visits (see section 4.2.4.5).

The Investigator is responsible for notification of the Sponsor on any event considered as unusual, even if this event may be considered as unexpected benefit for the study subject.

Adverse reactions

AR means “any unintended and unfavorable reaction of the body which may be related to the drug administration” (Federal Law dated 12.04.2010 No 61-Φ3 “On drug circulation”).

AR severity grades

AR severity grade will be established as per the below classification:

- **Grade 1: mild.** Asymptomatic (detected at physical or laboratory-instrumental investigation) or with minimally pronounced symptoms, easily tolerable by a subject, causing minimum discomfort and not interfering with normal activity, not requiring special treatment;

- **Grade 2: moderate.** Causing discomfort, limiting normal activity; requiring medical aid without invasive interventions (for example, applying a dressing);
- **Grade 3: severe.** Making normal activity impossible; disabling; requiring invasive intervention; requiring hospitalization; life-threatening; death.

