Causal relation of AR to administration of the study drugs

Causal relation of AR to administration of the study drugs will be evaluated based on criteria of the World Health Organization (WHO):

- **Definite.** Clinical manifestations of AR, including laboratory abnormalities, observed during administration of the drugs, which may not be explained by presence of current diseases and influence of other factors and chemical compounds. Side reaction manifestation regress after the drug withdrawal and develop after re-administration.
- **Probable.** Clinical manifestations of AR, including laboratory abnormalities, related to time of the drug administration, which are unlikely related to concomitant diseases or other factors and which regress after the drug withdrawal. Response reaction to re-administration is unknown.
- **Possible.** Clinical manifestations of AR, including laboratory abnormalities, related to time of the drug administration, which may be explained by presence of concomitant diseases or administration of the other drugs and chemical compounds. Information on reaction to withdrawal of the drug is unclear.
- **Unlikely.** Clinical manifestations of AR, including laboratory abnormalities, which develop with no clear temporary relation to the drug administration; there are other factors (drugs, diseases, chemical substances), that may be a reason of their development.
- **Conditional.** Clinical manifestations of AR, including laboratory abnormalities, related to “side reactions”, that require obtaining additional data (for accurate estimate) or these obtained data are analyzed at present.
- **Unclassified.** Reports on suspected side reaction may not be evaluated, because the information is not sufficient or it is contradictory.

Serious adverse reaction or unexpected adverse reaction

Serious AR (SAR) is an adverse reaction of the body related to the administration of the drug that led to death, congenital anomaly or birth defects or life-threatening, requiring hospitalization or incapacitating and (or) disabling (Federal Law dated 12.04.2010 No 61-Φ3 “On drug circulation”).

In case of SAR development in the study subject, administration of the study drug is discontinued, the Medical Investigator completes the respective section of the CRF of the study subject and SAR Report Form.

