If any AR develops, the Investigator should complete the respective sections of the CRF of the study subject, evaluate feasibility of continuing the study by female patient (exclude the study subject or continue participation of female patient in the study). ARs will be recorded from the moment of the study drug administration and to completion of the final visit (Visit 3).

For each AR, the following information should be recorded in the primary medical documentation:

- AR nature as per the ICD-10 terminology system (International Classification of Diseases 10th revision);
- severity grade (mild/ moderate/ severe AR);
- causal relation to administration of the test drug/reference drug (definite/ probable/ possible/ unlikely/ conditional/ unclassified);
- duration (start date and time / stop date and time);
- outcome (resolved/ resolving/ resolved with sequelae/ not resolved / lethal outcome/ no data);
- is AR serious.

Report on serious adverse reaction to the Sponsor

In case of SAR, it is necessary to record the fact of SAR development in the primary documentation and complete respective pages of the CRF of the study subject.

Information on SAR should be sent to the pharmacovigilance officer of JSC Pharmasyntez, [name] within 24 hours:

- [contact];
- [contact];
- E-mail: [contact].

A special form of serious adverse reaction is completed in this case (see section 17.1), original of which is sent to JSC Pharmasyntez to the following address: [name].

Notification form should be sent, even if the Investigator has incomplete volume of information on SAR. However, after the primary report on SAR, the Investigator should always inform on evaluation of degree of SAR relation to the administration of the study drug (see section 8.2). The Investigator should receive confirmation that the information is delivered.

If provided by the current requirements, the Sponsor will send respective notifications on AR to appropriate healthcare authorities.

Pregnancy during the study

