17.1 Serious adverse reaction report form

Site ID:	Protocol ID:
Principal Investigator/Coordinator:	Office phone No:
Information on patient:	ID: _____ Randomization ID: _____ Gender: M / F Birth date: ____ / ____ / ____ Previous participation in the clinical studies: yes / no
Information on the drug:	Name _____ Dose _____ Route of administration _____ Date of administration: ____ / ____ / ____ Time of administration: _____ hour _____ min
Brief description of adverse reaction:	
Report: primary / secondary _____	
SAR start date and time:	Date: ____ / ____ / ____ Time: _____ hour _____ min
SAR end date and time:	Date: ____ / ____ / ____ Time: _____ hour _____ min
Is SAR unexpected:	Yes / No
Criteria of AR seriousness:  death  life-threatening  hospitalization or its prolongation  persistent or significant disability/incapacity  congenital anomaly/birth defect  important from medical point of view	Causal relation of SAR to administration of the study drugs:  definite  doubtful  probable  conditional  possible  unrelated  unclassified
	Severity  mild  moderate  severe
Actions taken  withdrawal of patient from the study  hospitalization  drug or non-drug therapy for relief of SAR  no  other	SAR outcome:  recovered/resolved  recovering/resolving  recovered/resolved with sequelae  not recovered/not resolved  fatal  unknown  other
Additional information:	
Signature of the Investigator:	Date:

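### AR and SAR recording depends on a possible or actual drug relation, no all-cause event category is defined, and the causality scales in 8.2/8.3 and Annex 17.1 disagree

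*Protocol*

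**What the plan says.** Section 8.2 of the protocol takes both definitions from the federal law on drug circulation. An AR is "any unintended and unfavorable reaction of the body which may be related to the drug administration". For serious events the wording is stricter: "Serious AR (SAR) is an adverse reaction of the body related to the administration of the drug", followed by the seriousness criteria.

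Section 8.3 acts on these terms. CRF entry begins with an AR: "If any AR develops, the Investigator should complete the respective sections of the CRF of the study subject". The 24-hour notice to the sponsor begins with a SAR. For each AR the investigator then records "causal relation to administration of the test drug/reference drug (definite/ probable/ possible/ unlikely/ conditional/ unclassified"; that list has six grades and no *unrelated*. Section 8.2 describes the *unlikely* grade as covering manifestations "which develop with no clear temporary relation to the drug administration" where other causes are possible.

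The form in Annex 17.1 has its own list under "Causal relation of SAR to administration of the study drugs": definite, probable, possible, doubtful, conditional, unrelated and unclassified.

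Section 3.2 separates all ARs (objective 10: "To determine percentage of female patients with any adverse reactions") and all SARs (objective 11) from those graded definite, probable or possible (objectives 12 and 13). Section 9.1.4 lists six safety frequencies, starting with AR and SAR, and compares them between main and control groups by two-sided Fisher's exact test.

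**The concern.** In a placebo-controlled trial, the difference between randomised arms is the evidence on whether the drug causes an event. That evidence is cleanest when every untoward event is counted and the causality opinion is kept as a separate attribute. Here the opinion is part of the definition that decides whether an event is recorded.

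The setting makes this matter. Every patient has just had laparoscopic adhesiolysis, so attributing a post-operative complication to the surgery is natural and often correct. A site that follows 8.2 literally may decide that such an event is not an AR. If it is serious, the site may decide that it is not a SAR and that no 24-hour report is due. The statistical analysis plan cannot recover an event that was never entered.

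The mismatch between scales adds to the difficulty. An investigator who grades a serious event *unlikely* under 8.2 finds no such box on the form, and the form's *unrelated* box describes an event that the SAR definition excludes.

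**Working it through.** This is mainly a comparison of text. The protocol states no figure to reproduce.

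**Step 1. What each place requires or allows**

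| Place | Condition or options on drug relation |
|---|---|
| 8.2, AR definition | relation is possible |
| 8.2, SAR definition | relation is asserted |
| 8.2 and 8.3, causality grades | definite, probable, possible, unlikely, conditional, unclassified |
| 17.1, SAR form | definite, probable, possible, doubtful, conditional, unrelated, unclassified |
| 8.2, laboratory and instrumental deviations | become ARs on listed criteria, with no causality judgement required |
| 9.1.4, AR and SAR frequencies | inherit the 8.2 definitions |
| 9.1.4, other four frequencies (physical examination, laboratory, BP/heart rate, ECG) | none |

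**Step 2. What follows**

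- The SAR definition is narrower than the grades meant to describe it. A serious event graded *unlikely*, or ticked *unrelated* on the form, is not a SAR as defined.
- The AR definition is looser. Events graded *unlikely*, *conditional* or *unclassified* are recorded. Only an event judged to have no relation at all lacks a place in 8.2/8.3.
- Such an event can be noted when concomitant diseases are updated at Visits 1 to 3 (section 4.2.4.2), but those entries are not among the frequencies compared in 9.1.4.
- Two of the six compared frequencies are therefore exposed, and four are not.

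**Step 3. The Phase I counts in section 2.2.2**

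194 + 8 + 4 = 206 ARs. Shares: doubtfully related 194/206 = 94.2%, conditionally related 8/206 = 3.9%, possibly related 4/206 = 1.9%. All 206 were recorded as ARs, including the 194 at the low end. The counts show that most events may sit where the present definitions and scales are least clear. They do not show that such events get lost.

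**Step 4. Illustration of lost sensitivity (rates are assumptions, not in the protocol)**

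Assume 26 patients per arm (the planned randomisations per group), true proportions with an AR of 60% and 30%, and the same fraction f of those patients' ARs recorded in both arms. Power of the two-sided 5% Fisher test is the sum, over all outcome pairs (i, j) with p ≤ 0.05, of Bin(i; 26, 0.60f) × Bin(j; 26, 0.30f).

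| f | Recorded rates | Power |
|---|---|---|
| 1.00 | 60% v 30% | 48% |
| 0.75 | 45% v 22.5% | 31% |
| 0.50 | 30% v 15% | 16% |
| 0.25 | 15% v 7.5% | 5% |

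The direction is general: equal under-recording in both arms shrinks the difference and the power. The protocol gives no basis for choosing f.

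**The case against.** The strongest reply is that causality here is an attribute recorded after entry, not a test for entry. The AR definition asks only for a possible relation. Section 8.3 lists causality among the items noted for each AR, with grades well below *possible*. It requires the SAR form even when information is incomplete and places the causality assessment after the first report. The form's *unrelated* box shows that unrelated serious events were expected to be reported. Section 2.3.1 links expected AR incidence to the risks of the disease, surgery and anaesthesia. Section 8.2 sends only pre-dose symptoms to concomitant disease and asks for notice of any unusual event. The definitions also come from national law.

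Much of this stands, and it rules out three stronger readings:

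- *That ARs are restricted to drug-related events.* They are not; *unlikely*, *conditional* and *unclassified* events are recorded.
- *That objectives 10 and 12 nearly coincide.* They do not. In the Phase I event counts the contrast would be 206 against 4. The overlap is closer for objectives 11 and 13, and only on a literal reading of the SAR definition.
- *That most events of the Phase I kind would be left out.* Those events were recorded. The Phase I definitions are not shown, so the counts predict nothing either way.

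The reply does not remove the contradiction. The form and section 2.3.1 point to broad capture, while the SAR definition, which triggers the report, points the other way. Notice of unusual events is undefined in scope and does not feed the 9.1.4 frequencies. Nothing in the protocol suggests that the statutory definitions prevent wider collection.

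**Conclusion.** The point holds as a defect in definitions and a conflict between sections, with a real but unquantified consequence. It is clearest for serious events, where the definition contradicts both the lower causality grades and the form. For non-serious events the gap is limited to those judged to have no relation at all.

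One might infer that the safety comparison is biased in favour of the drug, or that it rests as a whole on a causality filter. The protocol supports neither. The trial is double-blind, so provided the blind between drug and placebo holds, under-recording should not depend on arm. The expected effect is fewer recorded events and less chance of seeing a true excess. Four of the six frequencies in 9.1.4 carry no causality condition.

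The size of the loss depends on how sites read 8.2 and cannot be derived from the protocol; the power figures above rest on assumed rates. The change is still worth making before data collection, because missed events cannot be restored at analysis.

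**What to change.** - In 8.2 and 8.3, state that every untoward event after dosing is recorded, and every serious one reported to the sponsor within the existing 24 hours, irrespective of assessed cause. The statutory AR and SAR definitions can stay as the description of the related subset.
- Use the causality grade only to form the subsets in objectives 12 and 13. Let objectives 10 and 11 and the first two frequencies in 9.1.4 count all recorded events.
- Use one causality scale, including *unrelated*, in 8.2, 8.3 and Annex 17.1.

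Cost: wording in two sections and one form, with matching wording in objectives 10 and 11 and section 9.1.4. Sites will have somewhat more events to record and report.

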2.6 Description of the study population

The study population will be hospitalized patients with confirmed diagnosis of pelvic adhesions. The study will include female patients aged from 18 to 45 years after signing informed consent. Patients meeting inclusion criteria, without non-inclusion criteria (sections 5.1 and 5.2), passed all the screening procedures, will be included into the study and randomized into one of the study groups

3 Purposes and objectives of the study

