4.2.1 Description of the study design

A multicenter randomized double-blind placebo-controlled clinical study of efficacy and selection of dose of the drug Seroguard, solution (JSC Pharmasyntez, Russia) used for prevention of pelvic adhesions will be performed.

After successful completion of screening procedures, a female patient will undergo a planned laparoscopic surgery. Randomization of female patients into groups will be performed on the day of surgery using an online IWRS system (Interactive Web Response System). The test drug or the placebo are used at the final stage of the surgery. A female patient is planned to be under control in the hospital for 6 days after completion of the surgery. On Day 7 of the study, a female patient may be discharged from the hospital, if there are no any contraindications, in this case a follow-up of a female patient is performed on outpatient basis. Follow-up lasts for 4 weeks, up to Day 28 of the study. Then a complete evaluation of treatment efficacy after repeated MRI-investigation of the abdominal cavity and the pelvis is performed.

Study procedures aimed at evaluating safety and efficacy of the test drug and the placebo will be identical in all the groups:

- 1) Placebo group, 1.5 mL/kg – up to 30 screened female patients which corresponds to 26 randomizations and 24 completed cases
- 2) Placebo group, 2.4 mL/kg – up to 30 screened female patients which corresponds to 26 randomizations and 24 completed cases
- 3) Seroguard group, 1.5 mL/kg – up to 30 screened female patients which corresponds to 26 randomizations and 24 completed cases
- 4) Seroguard group, 2.4 mL/kg – up to 30 screened female patients which corresponds to 26 randomizations and 24 completed cases

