9.1.4 Safety analysis

Descriptive part of safety analysis by primary endpoint will include evaluation of frequencies and bilateral 95% CI for the following primary endpoint parameters:

- AR – common frequency and frequency in separate groups (as per ICD-10)
- SAR - common frequency and frequency in separate groups (as per ICD-10)
- Frequency of clinically significant changes in results of physical examination – in general, for the study and by visits
- Frequency of clinically significant changes in parameters of laboratory investigations – in general, for the study and by visits
- Frequency of clinically significant changes in parameters of BP and heart rate – in general, for the study and by visits
- Frequency of clinically significant changes in ECG parameters – in general, for the study and by visits

Comparison of frequencies between main and control groups will be performed using Fisher's exact test (bilateral variant).

Analysis of the specified safety parameters will be performed for ITT and safety population (if it is different from ITT).

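### Section 8.2 leaves prolonged hospitalization and medically important events out of the definition of a serious adverse reaction, while the report form in 17.1 lists both

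*Protocol*

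**What the plan says.** Section 8.2 gives the definition that decides whether a reaction is serious. It covers death, congenital anomaly or birth defect, and reactions that are "life-threatening, requiring hospitalization or incapacitating and (or) disabling", and attributes the wording to the federal law on drug circulation. It mentions neither the extension of a hospital stay nor medically important events.

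The form in section 17.1 lists the same headings, but its hospital box reads "hospitalization or its prolongation", and it adds a box "important from medical point of view".

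The order of use is set in two places. Section 8.2 has the investigator fill in the case report form section and the report form when a SAR develops. Section 8.3 requires the information to reach the sponsor within 24 hours and adds: "A special form of serious adverse reaction is completed in this case (see section 17.1".

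The setting is inpatient. Section 2.6 states: "The study population will be hospitalized patients with confirmed diagnosis of pelvic adhesions". Section 4.2.1 states: "A female patient is planned to be under control in the hospital for 6 days after completion of the surgery", and then: "On Day 7 of the study, a female patient may be discharged from the hospital", provided nothing speaks against it.

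The classification feeds the analysis. Section 9.1.4 lists "SAR - common frequency and frequency in separate groups (as per ICD-10" among the safety frequencies and compares frequencies between the main and control groups by a two-sided Fisher's exact test.

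**The concern.** One protocol holds two lists of seriousness criteria, and the shorter one is applied first. An investigator who follows 8.2 to the letter may never open the form on which the wider criteria are printed.

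The mismatch matters more here than in an outpatient trial. The drug is given once, at the end of surgery, and each woman then remains in hospital by plan. During that stay, delayed discharge is a foreseeable consequence of a complication, and 8.2 does not name it.

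Two things depend on the label: whether the sponsor is told within 24 hours, and whether the event enters the SAR counts that serve objectives 11 and 13 in section 3.2 and the comparison in 9.1.4.

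**Working it through.** No figure in the plan needs to be reproduced. The check is a comparison of the two texts, followed by one ratio for scale.

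**Step 1. The two lists side by side.**

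| Criterion | Section 8.2 | Form, 17.1 |
|---|---|---|
| Death | yes | yes |
| Life-threatening | yes | yes |
| Hospitalization | yes | yes |
| Prolongation of a hospital stay | not named | yes |
| Disability or incapacity | yes | yes |
| Congenital anomaly or birth defect | yes | yes |
| Medically important | not named | yes |

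The form therefore has two grounds that 8.2 lacks. The form also qualifies disability as persistent or significant, which 8.2 does not; on that line the form is the narrower text.

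**Step 2. Which text comes first.** Sections 8.2 and 8.3 both make the form a consequence of having a SAR. The definition in 8.2 is the entry condition, so the form's extra boxes do not by themselves widen it.

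**Step 3. Which events change status.**

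- Fatal, life-threatening, incapacitating or disabling during the inpatient stay: serious under both texts.
- Starts during the stay and leads to readmission after discharge: serious under both, through hospitalization.
- Starts after discharge and leads to admission: serious under both.
- Only effect on seriousness is a longer stay: serious by the form, not by a literal reading of 8.2.
- Medically important and nothing else: serious by the form, not by 8.2, at any time in the study.

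Only the last two classes are affected.

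**Step 4. Length of the inpatient window.** The planned stay is 6 days (section 4.2.1). Visit 3 is at Day 30±4 (section 4.5).

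- At Day 30: 6/30 = 20%.
- At Day 34: 6/34 = 18%.
- At Day 26: 6/26 = 23%.

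This share applies to every dosed woman; 104 randomizations are planned (section 9.2). It measures time during which the prolongation gap is open. It does not count events.

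**Step 5. Number of events.** This cannot be derived. The only serious-event data are from Phase I (section 2.2.2): 4 serious reactions in three patients, with no statement of which criterion made them serious.

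**Step 6. Causality scales, a secondary point.** Sections 8.2 and 8.3 use six levels: definite, probable, possible, unlikely, conditional, unclassified. The form has seven: it drops *unlikely* and adds *doubtful* and *unrelated*. Because 8.2 defines a SAR as related to the drug, the *unrelated* box has no counterpart in the text.

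**The case against.** **A broader reading of 8.2.** A reaction that obliges a woman to stay in hospital can fairly be said to require hospitalization. On that reading prolongation is already covered. The reading is reasonable, but the text does not state it, and the sponsor's own form treats prolongation as something to spell out. It also does nothing for medically important events.

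**Statutory wording.** Section 8.2 attributes its definition to a federal law. That explains the origin of the wording; it does not remove the disagreement with the form.

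**Events are not lost.** Section 8.3 has every adverse reaction recorded with severity, causality, duration, outcome and a seriousness flag. Overall reaction frequency is analysed, severe reactions are a separate objective, and 8.2 asks investigators to notify the sponsor of anything unusual. This stands: what is at stake is the serious label and its reporting clock, for a narrow subset of events. The trial is also double-blind, and nothing suggests the mismatch would favour one arm.

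**Causality terms.** *Doubtful* and *unlikely* may be one category translated two ways, since the Phase I summary also speaks of doubtfully related reactions. Objective 13 counts only definite, probable and possible relations, so the differing levels do not alter it. The point is tidying, apart from the extra *unrelated* level.

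**Stronger readings that a reader might infer.** One could conclude that 8.2 excludes the commonest kind of serious event, in the period of highest risk. The protocol supports neither statement: it gives no breakdown of serious events by criterion and no risk by time. One could also conclude that an event in the inpatient week can meet the hospital criterion only through prolongation; later readmission contradicts that. Finally, one could picture some sites working from 8.2 and others from the form. All sites hold both texts, so inconsistent classification is possible but cannot be shown.

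**Conclusion.** The contradiction is real and worth correcting. Section 8.2 and the form in 17.1 disagree on two seriousness criteria, and the narrower text controls whether the form is opened. Events serious solely through a prolonged stay, or solely as medically important, could be missed in 24-hour reporting and in the SAR comparison.

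The conclusion assumes that 8.2 is read literally and applied before the form, which is the order sections 8.2 and 8.3 describe. The prolongation gap is open for the planned 6-day stay, roughly a fifth of follow-up; the medically important gap is open throughout. The number of events affected is unknown. The primary endpoint and the sample size are untouched.

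**What to change.** Reconcile section 8.2 with section 17.1 so that a single list of seriousness criteria applies in both places, including the form's prolongation and medically important criteria. The attribution to the federal law can stay, with the added criteria marked as the protocol's own. Settle the qualifier on disability at the same time.

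Secondarily, use one causality scale in 8.2, 8.3 and the form, and decide whether an *unrelated* level belongs on a form for reactions defined as drug-related.

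The cost is a wording change and possibly a few more expedited reports. No visit, assessment or sample-size figure changes.
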